10.4 STATISTICAL ANALYSES

10.4.1 General Approach

The response rate will be determined and reported along with a 95% confidence interval. Other time-to-event outcomes will be reported using Kaplan-Meier curves.

10.4.2 Analysis of the Primary Endpoints

Safety summaries will include summaries in the form of tables and listings. Reports will include the frequency (number and percentage) of treatment emergent AEs grouped by severity of the AE (per CTCAE, v5.0) and by relationship to study drug (e.g., either rhIL-15, obinutuzumab, or both).

Laboratory shift tables containing counts and percentages will be prepared by treatment assignment, laboratory parameter, and time. Summary tables will be prepared for each laboratory parameter. Figures of changes in laboratory parameters over time will be generated.

Results of vital sign assessments, ECGs, and physical exams will be tabulated and summarized.

Version Date: 09/14/2021

10.4.3 Analysis of the Secondary Endpoints

The duration of response (DOR; beginning at the date clinical response is first identified), overall survival (OS), event free survival (EFS), and progression free survival (PFS) will be estimated using Kaplan-Meier curves with appropriate confidence intervals reported.

Every report of response rates and time to progression should contain all patients included in the study. For the response calculation, the report should contain at least a section with all eligible patients. Another section of the report may detail the response rate for evaluable patients only. However, a response rate analysis based on a subset of patients must explain which patients were excluded and for which reasons. 95% confidence limits will be given.

10.4.4 Safety Analyses

The type, grade and frequency of toxicities will be reported.

10.4.5 Baseline Descriptive Statistics

Descriptive statistics (including means, standard deviations, and medians for continuous variables and proportions and CIs for discrete variables) will be used to summarize data as appropriate.

10.4.6 Planned Interim Analyses

No interim analyses are planned because of the single stage design of the trial.

10.4.7 Sub-Group Analyses

All secondary endpoints will be analyzed and reported separately for:

- patients with and without presence of del(17p)
- patients who do and do not have minimal residual disease (MRD)

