3.9 STUDY CALENDAR

	gui	əu				Study	Study Cycles	es			End of		Post-Treatment Follow-Un	ıt.
Procedure	Sereen	Basel			C				C2-6	,5	Disease Progression	Safety	Follow-Up (Prior to PD)	Survival (Post-PD)
Scheduling Window (Days):	-28 to	0-11	-142	4 (-1)	5 (-1)	8	11 18 (-1) (-1)	1 (-3)	4	∞	Treatment discon/PD ³	Day 30 (+7)	Every 3, 6, or 12 months^4	Every 3 months ⁵
Confirmation of Diagnosis	×													
Physical Exam and ECOG PS ⁶	×	×		×	×	×	X	×	×		×	×	×	
CBC with Differential	×	×	×	×	×	X	X	×	×		×	×	×	
Reticulocyte Count	×	×	×	×	×	×	×	×	×		×	×	×	
Chemistry Panels ⁷	×	×	X	×	×	×	X	×	×		X	X	X	
LDH, Uric Acid, Total Protein		×	×	×	×	×	X	×	×		X	×	X	
PT/INR and aPTT	×	×	X					×			X	X	X	
Thyroid Function (TSH, reflex T3, T4)	×	×	×					×			×			
Urinalysis	×	×	×					×			×			
Pregnancy Test (urine/serum; WOCBP)	×	×	×											
Hepatitis B and C, HIV Antibody, and Karvotype Testing	×													
HLA typing (A, B, C, DR, DQ), Anti- nuclear antibody (ANA), G6PD		×												
CMV, EBV, SPEP, C-reactive Protein (CRP), IGVH mutation analysis, PB		×									X (PD only)			
Interphase FISH panels. Iron panels Folate and B12		×	×		+		-	_						
Serum free light chains, Quantitative IgG		×	×								×	×	×	
Beta-2 microglobulin, Haptoglobin, DAT		×	×					×			×	X	×	
T, B, NK cell subsets		×						×			X	X	×	
CT Scans, Brain MRI ⁹	X	X									X		X	
Flow Cytometry, Bone Marrow Aspiration/Biopsy ¹⁰		X						od)	(post-C3 only)	only)	X			
EKG	X													
Symptoms/Adverse Events Assessment, Concomitant Medication Review	X	X						X			X	X	X	
Research Blood/Tissue Samples ¹¹		×	X	X	×	X		×		×	X	X	X	
Survival Status														×

NOTE: Any other tests should be performed as clinically indicated. See Section 3.4 for drug administration information. See Section 5 for information on research blood samples/correlative studies to be collected.

suspicion for HIV as determined by PI; Hepatitis B and C, karyotype, EKG, PB interphase FISH, and bone marrow aspiration/biopsy (all within 3 months) ¹ Screening and Baseline evaluations should be performed within 28 days prior to enrollment and dosing, respectively, unless otherwise noted and with the following exceptions: Confirmation of diagnosis (no time limit); HIV antibody (at any time, or within 3 months in patients with high risk or clinical NOTE: Any screening tests performed within the specified time frame for baseline do not need to be repeated.

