6.3.3 Progression-Free Survival

Progression-free survival (PFS) is defined as the duration of time from the date of study enrollment until time of disease relapse, disease progression, or death, whichever occurs first.

A Group A criteria define the tumor load. Group B criteria define the function of the hematopoietic system or marrow. For CR, all of the criteria have to be met.

^B Sum of the product (SPDs) of up to 6 lymph nodes as evaluated by CT scans. If CT is unavailable, the absence of enlarged lymph nodes (> 1.5cm) documented by physical exam is acceptable. For progression, SPDs should increase by >50% and at least one of the target lesions should be pathologically enlarged (> 1.5cm).

^C Complete response requires confirmation with bone marrow biopsy.

^D For progression, absolute lymphocyte count should increase ≥ 50% from nadir confirmed with two consecutive assessments within 3 months. CD19 B cell count should be >5,000/μL in at least one of the two assessments. Abbreviations and definitions:

Version Date: 09/14/2021

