6.3.4 Event-Free Survival

Event-free survival (EFS) is defined as the duration of time from the date of study enrollment until time of disease relapse, disease progression, alternative therapy for lymphoma given (such as radiation), or death, whichever occurs first.

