10 STATISTICAL CONSIDERATIONS

10.1 STATISTICAL HYPOTHESIS

- Primary Endpoints:
 - Maximum tolerated dose (MTD) of rhIL-15 administered intravenously for 5 days in combination with obinutuzumab
 - Frequency (number and percentage) of treatment-emergent AEs
- Secondary Endpoints:
 - o Overall response rate (including CR, CRi, and PR)
 - o Proportion of patients who are MRD-negative
 - o Duration of response (for patients who do and do not achieve MRD-negativity)
 - o Progression-free, event-free, and overall survival

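### Section 10.4.7 splits PFS, EFS and OS by MRD status, which is known only after treatment starts, without a landmark; the MRD-negative curve can look better by construction

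*Combined protocol and SAP*

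**What the plan says.** Section 10.4.7 states "All secondary endpoints will be analyzed and reported separately for" two pairs of subgroups: patients with and without del(17p), and "patients who do and do not have minimal residual disease (MRD"). Section 10.1 lists the secondary endpoints: overall response rate, the MRD-negative proportion, "Duration of response (for patients who do and do not achieve MRD-negativity"), and PFS, EFS and OS. Its wording treats MRD-negativity as something reached on treatment, and Section 1.1.2 groups MRD with response as a measure of antitumor activity.

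The clocks start earlier. Section 6.3.3 defines PFS as "the duration of time from the date of study enrollment until time of disease relapse, disease progression, or death, whichever occurs first". Section 6.3.4 measures EFS "from the date of study enrollment until time of disease relapse, disease progression, alternative therapy for lymphoma given", or death. No origin is given for OS.

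On method, Section 10.4.1 says "Other time-to-event outcomes will be reported using Kaplan-Meier curves", and Section 10.4.3 says DOR, OS, EFS and PFS "will be estimated using Kaplan-Meier curves with appropriate confidence intervals reported". Section 10.4.3 also wants reports of response rates and time to progression to cover all patients, but does not say which MRD group a patient without a reading joins.

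No section names the MRD sample, threshold or reading time. The likely source, by inference, is the peripheral blood flow cytometry that footnote 10 of Section 3.9 schedules at baseline and after cycles 3 and 6. The calendar row "Flow Cytometry, Bone Marrow Aspiration/Biopsy" also appears to carry a mark at treatment discontinuation or progression, although that table is broken in the text available.

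**The concern.** The del(17p) split uses a baseline factor and raises no difficulty. The MRD split does, because the group is defined by something observed after the clock starts. To be read as MRD-negative after cycle 3 or 6, a patient generally has to reach that visit without an event. If patients who progress or die earlier are placed in the other group, the MRD-negative group carries guaranteed event-free time and the other group absorbs all the early events. The curves then separate even when MRD has no prognostic value.

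Leaving unread patients out of both groups changes the problem. With one fixed reading the groups become comparable, but both curves measured from enrollment look better than PFS in the whole trial.

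OS is affected in the same way if its origin precedes the reading, though less so if early deaths are fewer than early progressions. DOR is affected only if MRD is read after the response date. That is unlikely where response depends on the post-cycle-6 CT (Sections 3.9, footnote 9, and 6.3).

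Separately, the MRD-negative proportion is itself a secondary endpoint. Splitting it by MRD status returns 100% and 0%.

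**Working it through.** The plan gives no figure for the MRD split, so there is nothing of its own to reproduce. The calculation below asks how large the artefact would be if MRD had no prognostic value.

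**Inputs from the documents.** Cycles last 28 days (Section 3.1), so the post-cycle-6 reading falls at about day 168 (m = 168/30.4375 = 5.52 months) and the post-cycle-3 reading at about day 84 (2.76 months). Accrual is capped at 24 (Section 10.2).

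**Inputs assumed.** Section 1.2.6 gives only response rates for obinutuzumab alone in previously treated patients (32% and 15%). PFS is therefore taken as exponential with median M = 12 months, and MRD status as independent of PFS. Three shares are varied:

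- p: share MRD-negative among those read (0.30 unless stated)
- a: share of unread early-event patients counted as not MRD-negative, the rest being left out
- c: share of early events dated at the reading visit itself, so that the patient is still read

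**Formulas.** S(t) = exp(−ln 2 · t/M), and the share read is R = S(m) + c(1 − S(m)). PFS at 12 months is then:

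- MRD-negative: S(12)/R
- Not MRD-negative: (1 − p)S(12) / [(1 − p)R + a(1 − R)]

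**Upper case (a = 1, c = 0).** S(5.52) = 0.727 and S(12) = 0.500. MRD-negative: 0.500/0.727 = 0.688. Not MRD-negative: 0.70 × 0.500 / (0.70 × 0.727 + 0.273) = 0.350/0.782 = 0.448.

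| Handling of early events | MRD-negative | Not MRD-negative | Gap |
|---|---|---|---|
| Day 168, all in the not-negative group | 0.688 | 0.448 | 0.240 |
| Same, p = 0.15 | 0.688 | 0.477 | 0.211 |
| Half in that group, half left out (a = 0.5) | 0.688 | 0.542 | 0.146 |
| Half dated at the reading (a = 1, c = 0.5) | 0.579 | 0.472 | 0.107 |
| Both of these (a = 0.5, c = 0.5) | 0.579 | 0.520 | 0.059 |
| All dated at the reading (c = 1) | 0.500 | 0.500 | 0 |
| All left out, one fixed reading (a = 0, c = 0) | 0.688 | 0.688 | 0 |
| Day 84, all in the not-negative group | 0.586 | 0.470 | 0.116 |
| Day 84, half dated at the reading | 0.540 | 0.485 | 0.055 |

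PFS at 12 months in all patients is 0.500 throughout. In the upper case with other medians, the pair is 0.473 against 0.208 for 6 months and 0.829 against 0.665 for 24 months.

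**Negative at either reading counts, never-read patients left out.** With half of the 30% already negative at day 84 and S(2.76) = 0.853:

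- MRD-negative: 0.30 × 0.500 / (0.15 × 0.853 + 0.15 × 0.727) = 0.150/0.237 = 0.633
- Not MRD-negative: 0.70 × 0.500 / (0.853 − 0.237) = 0.568
- Gap: 0.065

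**At the trial's size.** In simulated trials of 24 patients with no true MRD effect, omitting trials with an empty group, the observed 12-month PFS behaves as follows:

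| Case | MRD-negative higher | Higher by at least 20 points |
|---|---|---|
| Upper case (5.2 MRD-negative patients on average) | 82% | 58% |
| Day 168, c = 0.5 | 65% | 36% |
| Day 84, c = 0.5 | about 57% | about 27% |
| Landmark at day 168 | about 50% | about 24% |

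The mean gap with the landmark is zero. With p = 0.15 in the upper case there are on average 2.6 MRD-negative patients, and 25% of trials have none or one.

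**The case against.** The strongest reply is that the bias needs an allocation rule the plan does not contain. Kaplan-Meier is compatible with a landmark start, so the section is silent rather than wrong. This is fair: the gap is conditional, and the 0.24 is an upper case.

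Flow cytometry at progression does not by itself put early progressors in the not-negative group. Their result does. If MRD is unrelated to outcome and every early event is dated at a reading, the gap is zero. That stands as a limiting case, but nothing in the plan secures it. If readings taken at progression are mostly positive, grouping depends on the outcome in another way.

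CT is scheduled only at baseline and after cycle 6, so some progression will be dated at that visit. A post-cycle-3 reading also roughly halves the gap. Both points reduce the size. Blood counts and symptoms can still show earlier progression.

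The MRD source is not named. Circulating tumor DNA with VDJ sequencing (Sections 5.1 and 5.3.4) is another candidate, and a landmark cannot be written until the source is fixed. That also stands, but the MRD endpoint needs the same definition in any case.

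Finally, this is a 3 + 3 trial with no test planned between MRD groups and perhaps five MRD-negative patients. That limits the harm. It does not make a prespecified split with a built-in advantage worth keeping.

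**Conclusion.** The concern holds as a conditional statement. None of the allocation rules examined that the plan's silence allows favours the not-MRD-negative group when MRD has no effect. The result is an advantage for the MRD-negative curve, or both curves lifted above the all-patient curve (0.69 in each against 0.50), or no artefact if every early event happens to be dated at the reading.

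The size rests wholly on assumed PFS, MRD rate and reading time. With a 12-month median and 30% MRD-negative, the spurious 12-month gap runs from 0 to 0.24, with several plausible cases between 0.06 and 0.15. The circularity of the MRD-by-MRD split needs no assumption.

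The consequence is confined to descriptive PFS, EFS and OS curves in at most 24 patients. The change should be made because it is cheap and the curves could be read as evidence that MRD predicts outcome. It has no bearing on the MTD or the adverse event conclusions.

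**What to change.** In Section 10.4.7, replace the MRD split of PFS, EFS and OS (and of DOR where the MRD reading follows first response) with a landmark analysis:

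1. Time zero is a named MRD assessment, for example the post-cycle-6 flow cytometry, with post-cycle-3 as a sensitivity analysis.
2. Include patients who have a result at that assessment and are event-free for the endpoint concerned (alive for OS, still in response for DOR).
3. Group by that result. Later readings do not move a patient.
4. Report how many patients are excluded and why.

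Drop the MRD-negative proportion by MRD status. Keep the del(17p) split and the all-patient curves as they are.

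The cost is wording only if the scheduled flow cytometry is the MRD source; otherwise the sample must be named first. Patients with an event before the landmark leave this one comparison. At day 168 that is 1 − S(5.52), or about 15%, 27% or 47% (3.5, 6.6 or 11.3 of 24) for assumed median PFS of 24, 12 or 6 months. The landmark removes the bias but not the imprecision: about 24% of simulated trials with no true difference still show the MRD-negative group at least 20 points higher, and the report should say so.

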10.4.8 Tabulation of Individual Participant Data

None.

10.4.9 Exploratory Analyses

The exploratory objectives such as seeking to identify potential biomarkers or T-cell and B-cell clones in peripheral blood which are associated with response, will be assessed using descriptive statistics as well as non-parametric methods such as exact Wilcoxon rank sum tests. The analyses will be done without formal adjustment for multiple comparisons, but in the context of the number of tests performed.

11 COLLABORATIVE AGREEMENTS

11.1 AGREEMENT TYPE

An MTA with Division of Cancer Treatment and Diagnosis (DCTD) for the IL-15 was executed on June 8, 2018.

12 HUMAN SUBJECTS PROTECTIONS

12.1 RATIONALE FOR SUBJECT SELECTION

CLL is a rare neoplasm that comprises a substantial proportion of all leukemia in middle-aged persons and is the most common type among elderly persons in western populations. Epidemiologic studies suggest that distribution by gender will be 66% males and 33% females(55). CLL is more common in Caucasian and African-American but rare in Hispanics and very rare in the Asian population. This study will be open to all patients who fit the inclusion criteria and

Version Date: 09/14/2021

provide informed consent to protocol participation. We would predict that distribution should be comparable to that seen on the NCI screening protocol as follows:

by gender: 33% women; 66% menby age: ages 23-79, median 60

• by race: 2% Asian, 11% Black, 8% Hispanic, 79% White

Subjects with HIV infection will be excluded due to potential toxicity and unknown effects of rhIL-15 and obinutuzumab on the underlying HIV infection and interference with ART. Because there is no significant preclinical information regarding the risks to a fetus or a newborn infant, all pregnant or breastfeeding woman will be excluded from participation in this trial.

12.2 PARTICIPATION OF CHILDREN

CLL is uncommon in patients under 45 years of age and is virtually unheard of in patients under 20 years of age. At the time of diagnosis, more than 95% of patients are 45 years old and above (1, 56). CLL may also be, biologically, a different disease in children. rhIL-15 has not been studied in human subjects under 18 years of age. For these reasons, individuals < 18 years old have been excluded from protocol participation.

12.3 PARTICIPATION OF SUBJECTS UNABLE TO GIVE CONSENT

Adults who are unable to consent are excluded from enrolling in this protocol. However, reconsent on this protocol may be necessary and there is a possibility that subjects could become decisionally impaired. For this reason and because there is a prospect of direct benefit from research participation (Section 12.5), all subjects ≥ age 18 will be offered the opportunity to fill in their wishes for research and care, and assign a substitute decision maker on the "NIH Advance Directive for Health Care and Medical Research Participation" form so that another person can make decisions about their medical care in the event that they become incapacitated or cognitively impaired during the course of the study.

Note: The PI or AI will contact the NIH Ability to Consent Assessment Team (ACAT) for evaluation as needed for the following: an independent assessment of whether an individual has the capacity to provide consent; assistance in identifying and assessing an appropriate surrogate when indicated; and/or an assessment of the capacity to appoint a surrogate. The PI or AI will obtain permission for decisionally-impaired adults via their appointed surrogate decision-maker or another legally authorized representative (such as legal guardian or holder of the durable power of attorney; i.e., DPA).. For those subjects that become incapacitated and do not have pre-determined substitute decision maker, the procedures described in NIH HRPP SOP 14E for appointing a surrogate decision maker for adult subjects who are (a) decisionally impaired, and (b) who do not have a legal guardian or durable power of attorney, will be followed.

12.4 EVALUATION OF BENEFITS AND RISKS/DISCOMFORTS

For patients with relapsed/refractory CLL, complete response rates for the six drug and drug combinations approved are no greater than 30%. Obinutuzumab, a humanized type 2 anti-CD20, is approved in combination with chlorambucil for CLL, and is thought to directly activated ADCC. Agents that may enhance ADCC, such as rhIL15, could improve efficacy of obinutuzumab. Although the clinical benefit of these drug(s) has not yet been established, the intent of offering this treatment is to provide a possible therapeutic benefit, and thus the patient will be carefully monitored for tumor response and symptom relief in addition to safety and tolerability.

Version Date: 09/14/2021

Since fevers, rigors, lymphopenia, LFT elevations, and thrombocytopenia occurred during IL-15 infusion in the continuous IV trial, and since obinutuzumab will be given concomitantly, these toxicities may overlap. However, all IL-15-related reactions were transient and resolved by Day 8 of each cycle (third post-infusion day). Obinutuzumab manufacturer recommendations for IRR and TLS prophylaxis and criteria for discontinuing therapy in the event of either will be followed.

12.5 RISKS/BENEFITS ANALYSIS

The currently approved regimens for relapsed/refractory CLL are not adequate, and the proposed drug combination of IL-15 and obinutuzumab has the prospect of benefitting this patient population.

There have been no studies of IL-15 in patients with HIV on or off ART. Two non-human primates with SIV who were not on ART and received rhIL-15 on Study 2078-10804 both died, while subsequent animals who received viral suppression were seemingly unaffected. rhIL-15 may therefore contribute to morbidity/mortality in patients with a detectable viral load. Since potential toxicity of IL-15 and obinutzumab may interfere with ART adherence and optimal viral suppression, patients with HIV may be exposed to additional toxicity for unknown potential benefit of IL-15 and should therefore be excluded from participating in this study.

12.5.1 Risks related to CT scans

CT scans often use a contrast agent. There is a small risk of having a reaction to the contrast and most often include nausea, pain in the vein where the contrast is given, headache, metallic and/ or bitter taste in the mouth and a warm, flushing feeling. Rarely, some people have more severe allergic reactions to the contrast which may include skins rashes, shortness of breath, wheezing or low blood pressure.

12.5.2 Risks related to MRI scans

During part of the MRI participants may receive gadolinium, a contrast agent, through an intravenous (iv) catheter. The risks of an IV catheter include bleeding, infection, or inflammation of the skin and vein with pain and swelling.

Mild symptoms from gadolinium infusion occur in fewer than 1% of those who receive it and usually go away quickly. Mild symptoms may include coldness in the arm during the injection, a metallic taste, headache, and nausea. In an extremely small number, fewer than one in 300,000 people, more severe symptoms have been reported including shortness of breath, wheezing, hives, and lowering of blood pressure.

Participants with kidney disease are at risk for a serious reaction to gadolinium contrast called "nephrogenic systemic fibrosis" which has resulted in a very small number of deaths.

The FDA recently issued a safety alert that indicates small amounts of gadolinium may remain in the body for months to years. The effects of the retained gadolinium are not clear. At this time, retained gadolinium has not been linked to health risks in people whose kidneys work well.

